11.1.2 Primary Effectiveness Endpoint

Time to Ambulation (TTA): Defined as elapsed time (in hours) between removal of the MYNX CONTROL[™] Venous Vascular Closure Device 6F-12F device (device group) or of the final sheath (control group) and when subject stands and walks 20 feet without evidence of rebleeding from any femoral venous access site.

Time to Hemostasis (TTH): Defined as elapsed time (in minutes) between removal of each MYNX CONTROL[™] Venous Vascular Closure Device 6F-12F device (device group) or of each sheath (control group) and first observed and confirmed venous hemostasis (per access site analysis).

- 11.2 Secondary Endpoints
- 11.2.1 Secondary Safety Endpoint

Rate of CEC adjudicated combined **minor** venous access site closure related complications within 30 days post-procedure, attributed directly to VCD or manual compression without other likely cause. Types of minor complications include:

Version: 3.0 / 31Jan2023

- Pseudoaneurysm Treated with thrombin injection, fibrin adhesive injection, or ultrasound guided compression and documented by ultrasound
- Pseudoaneurysm Not requiring treatment
- Arteriovenous fistula requiring treatment, documented by ultrasound
- Arteriovenous fistula not requiring treatment, documented by ultrasound
- Access site-related Hematoma > 6 cm documented by ultrasound
- Access site-related bleeding requiring > 30 min to achieve hemostasis
- Late access site-related bleeding (following hospital discharge eligibility)
- Transient loss of ipsilateral lower extremity pulse
- Ipsilateral deep vein thrombosis documented by ultrasound
- Transient access site-related nerve injury
- Access site-related vessel laceration
- Access site wound dehiscence
- Localized access site infection confirmed by culture and sensitivity, treated with intramuscular or oral antibiotics- Minor,
- Local access site inflammatory reaction Minor
- Allergic reaction
- Ecchymosis

11.2.2 Secondary Effectiveness Endpoints include the following:

Time to Discharge Eligibility: defined as elapsed time (in hours) between removal of the final MYNX CONTROL[™] Venous Vascular Closure Device 6F-12F device (device group) or removal of the final sheath (control group) and when subject is eligible for discharge from the institution based on the assessment of the attending physician.

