16.4 Statistical Hypotheses for Endpoints

Primary Effectiveness Endpoint- Primary efficacy will be measured using co-primary endpoints consisting of Time to Ambulation (TTA) and Time to Hemostasis (TTH) as defined below:

• **Time to Ambulation (TTA)**-Defined as elapsed time (in hours) between removal of the final VCD (device group) or of the final sheath (control group) and when subject stands and walks 20 feet without evidence of rebleeding from any femoral venous access site.

The null and alternative hypotheses of the primary effectiveness comparison for TTA are given below

Ho: $\mu_{Mynx \ Control} \geq \mu_{manual \ compression}$

Ha: $\mu_{Mynx \ Control} < \mu_{manual \ compression}$

Where μ_x is the average time to ambulation for the specified group

• Time to **Hemostasis (TTH)**- Defined as elapsed time (in minutes) between removal of each VCD (device group) or of each sheath (control group) and first observed and confirmed venous hemostasis (per access site analysis)

The null and alternative hypotheses of the primary effectiveness comparison for TTH are given below:

Ho: $\mu_{manual \ compression} - \mu_{Mynx \ Control} \leq 5$

Ha: $\mu_{manual \ compression} - \mu_{MynxControl} > 5$

Where μ_{xx} is the mean time to hemostasis for the indicated group and 5 minutes is the superiority margin.

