16.9.1 Primary Analysis

Efficacy

The primary efficacy endpoints will be analyzed separately.

The average time to ambulation in each treatment group will be compared using a standard T-test.

The average time to hemostasis will be compared to the treatment groups using a generalized linear mixed model where subject is considered a random effect with multiple access sites. The times to hemostasis in the manual compression group will be reduced by 5 minutes to account for the hypothesis that the time to hemostasis for the MYNX CONTROL[™] Venous VCD is at least 5 minutes less than manual compression. The analysis will consist of testing the coefficient on the fixed effect for treatment group. If that coefficient is found to be significantly different from zero, then the direction will be evaluated to assure that the hemostasis time is reduced on average when using MYNX CONTROL [™] Venous VCD.

Safety

The safety analysis will be completed on a per-limb basis.

This endpoint will be analyzed using a GEE approach for a logistic regression model with a compound symmetric working covariance structure where occurrence of an AE is the binary response variable and treatment group is the only explanatory variable. Least square means for each treatment group and the risk difference between groups will be calculated along with the two-sided 95% confidence interval. The one-sided 97.5% confidence bound (equivalent to the appropriate bound from the two-sided 95% interval) will be compared to the non-inferiority window. If the upper bound is less than the non-inferiority window, then the two treatment groups will be considered non-inferior relative to the proportion of limbs experiencing a major venous access site closure-related complication.

As a supplementary analysis, a generalized linear mixed model will be used where subject will be entered into the model as a random effect and a compound symmetric correlation structure applied to those subjects contributing two limbs.

Version: 3.0 / 31Jan2023

Trial Success

This trial will be considered a success if both primary efficacy endpoints and the primary safety endpoint are achieved.

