8.5 Analyses of Effectiveness Endpoints

8.5.1 Primary Effectiveness Endpoint Analysis

There are two co-primary effectiveness endpoints: Time to hemostasis, and time to ambulation.

The average time to ambulation in each treatment group will be compared using a standard T-test. The test will be done on a per subject basis. The null and alternative hypotheses are:

Ho: $\mu_{Mynx \ Control} \geq \mu_{manual \ compression}$

Ha: $\mu_{Mynx \ Control} < \mu_{manual \ compression}$

where μ_x is the average time to ambulation for the specified group. A p-value for this one-sided test less than 0.025 will indicate that the time to ambulation for the subjects using the MYNX CONTROLTM Venous VCD was significantly less than for those where manual compression was used.

The average time to hemostasis will be analyzed on an access site level. The null and alternative hypotheses of the primary effectiveness comparison for TTH are given below:

Ho: $\mu_{manual \ compression} - \mu_{Mynx \ Control} \le 5$ Ha: $\mu_{manual \ compression} - \mu_{Mynx \ Control} > 5$

where μ_x is the mean time to hemostasis for the indicated group and 5 minutes is superiority margin.

The average time to hemostasis will be analyzed using a generalized linear mixed model where subject is considered a random effect with multiple access sites and treatment group is a fixed effect. The times to hemostasis in the manual compression group will be reduced by 5 minutes to account for the hypothesis that the time to hemostasis for the MYNX CONTROL[™] Venous VCD device is at least 5 minutes less than manual compression. The analysis will consist of testing the coefficient on the fixed effect for treatment group. If that coefficient is found to be significantly different from zero, then the direction will be evaluated to assure that the hemostasis time is reduced on average when using MYNX CONTROL[™] Venous VCD. This test is by default a two-sided test, so a p-value of 0.05 or less with the direction of the difference showing shorter times for MYNX

CONTROL[™] Venous VCD will correspond to a one-sided test at the 0.025 level results in achieving this endpoint.

If the distribution assumptions (normality, lognormality) for the primary effectiveness endpoints do not hold based on Shapiro-Wilk test at the 0.05 alpha level, a non-parametric Wilcoxon rank sum test will be used to compare the treatment groups.

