8.8 Analysis of Roll-in Subjects

Roll-in subjects will be summarized using descriptive statistics. No formal hypothesis testing will be done on this group.

Time to ambulation will summarized using the mean, median, standard deviation, sample size, minimum, and maximum. A 95% confidence interval for the average time to hemostasis will be calculated using the T-distribution.

Time to hemostasis will first be summarized across access sites within each subject by calculating the mean time to hemostasis by averaging the individual site-specific times. Time to hemostasis will then be summarized across subjects by calculating the mean, median, standard deviation, sample size, minimum, and maximum. A 95% confidence interval for the average time to hemostasis will be calculated using the T-distribution.

The proportion of roll-in subjects experiencing a major access related complication will be calculated along with a 95% confidence interval constructed using the Clopper-Pearson method.

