11 HANDLING OF MISSING DATA

While all reasonable efforts will be made to obtain the data required to evaluate this endpoint, it is expected that some subjects may not be able to provide data due to several reasons (loss to follow-up, study withdrawal, death). For all primary and secondary analyses, no imputation of missing data is planned. Subjects who have ascertainment of status at a later out-of-window date (for example, subjects who are known to be free of events past discharge but missed the discharge visit) are not considered missing as their status is known and their data will be used as noted previously. The primary endpoint rate will be calculated as the number of subjects who had an event prior to the milestone visit divided by the number of evaluable subjects who had sufficient follow up (e.g., at least discharge visit) plus any subjects who had an event prior to the milestone visit.

A sensitivity analysis will be conducted for the endpoints of time to hemostasis, time to ambulation, and time to discharge eligibility using a simple pattern mixture model approach. For each treatment group, the overall mean is a weighted average of the observed data and the unobserved data. Assumptions on the unobserved data need to be used in order to assess the sensitivity of the study conclusions. For the control group, the mean of the unobserved data will be set equal to that of the observed data essentially assuming the missing data are missing at random. For the MYNX CONTROLTM Venous VCD group, the mean of the unobserved data will be incrementally increased by a pre-specified Δ until the overall interpretation of the endpoint changes. For time to hemostasis, the mean of the unobserved data will be increased in increments of 1 minute. For time to ambulation and time to discharge eligibility, Δ will be increased in increments of 0.5 hour. Once Δ has increased to the point that the endpoint conclusions change, then the feasibility of that increase will be assessed from a clinical standpoint.

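### SAP 8.5.1 gives no response scale for the co-primary TTH model, and can replace it with a Wilcoxon test that has no clustering adjustment and does not in general test the 5-minute mean difference

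*SAP*

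**What the plan says.** **Hypothesis.** Protocol 16.4 and SAP 8.5.1 test whether mean TTH on manual compression exceeds mean TTH on the device by more than 5 minutes. In Protocol 16.4 the parameter "is the mean time to hemostasis for the indicated group and 5 minutes is the superiority margin".

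**Unit and model.** SAP 8.5.1: "The average time to hemostasis will be analyzed on an access site level". Protocol 16.9.1: "The average time to hemostasis will be compared to the treatment groups using a generalized linear mixed model", with subject as a random effect. Neither section names a distribution, link or transformation.

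**Margin.** SAP 8.5.1: "The times to hemostasis in the manual compression group will be reduced by 5 minutes to account for the hypothesis". The treatment coefficient is then tested against zero. A two-sided p-value of 0.05 or less in the right direction counts as success.

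**Switch.** SAP 8.5.1 adds a rule covering both co-primary effectiveness endpoints: where their assumptions (it lists normality and lognormality) "do not hold based on Shapiro-Wilk test at the 0.05 alpha level, a non-parametric Wilcoxon rank sum test will be used". Protocol 16.9.1 contains no such rule.

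**Sample size.** SAP 5 and Protocol 16.8 assume lognormal times with means of 6 and 13 minutes. They calculate power on logs and report about 95% with 150 subjects (100:50). The SAP assumes 3 sites per subject, with variation between sites about half of that between subjects. No SD is printed.

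**Consequence.** Protocol 16.9.1 requires both effectiveness endpoints and the safety endpoint for trial success.

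**The concern.** Two things a confirmatory test needs are left open or lost.

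1. **Scale.** Minutes fit the hypothesis, the subtraction of 5, and SAP 11: "For time to hemostasis, the mean of the unobserved data will be increased in increments of 1 minute". Logs fit the mention of lognormality in SAP 8.5.1. They also fit SAP 9 and Protocol 16.9.6, whose poolability checks refer back to the model in the sample size sections. The two scales give different tests.

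2. **Fallback.** The mixed model targets the mean difference and allows for correlated sites. An ordinary rank sum test applied at the stated access-site level treats sites in one subject as independent, and in general it does not test a difference in means. If the 5-minute shift is not carried over, the margin is lost as well.

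The result of a required endpoint could then turn on choices made after the data of an open-label trial exist, and on a test whose error rate for the stated hypothesis is not controlled.

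**Working it through.** **Inputs from the documents.** Means 6 and 13 minutes, margin 5, one-sided 2.5%, 3 sites per subject, allocation 136:68 (100:50 for the stated TTH power).

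**Assumptions.** The site-to-subject ratio of one half is read as variances, so ICC = 1/(1 + 0.5) = 0.67; if SDs are meant, ICC = 1/(1 + 0.25) = 0.80. The 5-minute shift is kept in the rank test. Log SDs are between-subject unless stated otherwise; they are assumed, because the documents give none.

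**1. The stated 95% power.** The SD of a subject mean is SD × √(1 + 0.5/3) = 1.080 × SD. The standard error multiplies this by √(1/100 + 1/50) = 0.1732. For 95% power, effect/SE must be 1.960 + 1.645 = 3.605. Three readings meet this:

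| Effect | Between-subject SD needed |
|---|---|
| ln(8/6) = 0.288 (shift, then log) | 0.427 |
| ln(13/6) = 0.773 (log, no shift) | 1.15 |
| 2 minutes beyond the margin | 2.97 minutes |

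The documents do not say which was used, so the figure can be neither confirmed nor refuted. The value 0.427 is one point in a range.

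**2. Log scale with the shift.** Control times of 5 minutes or less have no logarithm after 5 is subtracted. With mean 13 and a total site-level log SD of 0.40, 0.52 or 0.60, these are 1.4%, 5.9% or 9.8% of control sites. No rule covers them. The log coefficient matches the stated hypothesis when control minus 5 has the device distribution, but not in general.

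**3. How often the switch fires.** In simulated lognormal data, Shapiro-Wilk rejected in 100% of trials on minutes. On unshifted logs it rejected in about 20-24%, counting rejection in either arm, and in about 9-14% for the device arm alone.

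**4. Clustering under a pure 5-minute shift.** Design effect = 1 + (3 − 1) × 0.667 = 2.33. One-sided error = P(Z > 1.96/√2.33) = P(Z > 1.283) = 10.0%. At ICC 0.80 the design effect is 2.6 and the error 11.2%. Simulation of the site-level Wilcoxon gave about 9-11%; one value per subject gave about 2-3%.

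**5. Target of the test, both arms lognormal with means 6 and 11.** The true difference is exactly 5. Total log variance is 1.5 times the between-subject log variance, and median = mean × exp(−total variance/2). The medians below only indicate direction.

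- Equal log SD 0.427: total variance 0.2735, factor 0.872. Device median 5.23; shifted control 9.59 − 5 = 4.59. The rank test leans against the device.
- Log SD 0.5 device, 0.3 control: factors 0.829 and 0.935. Device median 4.97; shifted control 10.28 − 5 = 5.28. It leans towards the device.

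Simulated one-sided error, nominal 2.5%:

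| Log SD device/control | Site-level Wilcoxon | Subject-level Wilcoxon |
|---|---|---|
| equal, 0.3 to 0.6 | 1.8% down to 0.1% | 0.0-0.8% |
| 0.4/0.3 | 4.0% | 1.2% |
| 0.5/0.3 | 11.6% | 3.5% |
| 0.6/0.3 | 29.1% | 9.6% |
| 0.3/0.5 | 0.0% | 0.0% |

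A test on minutes with arm-specific variances stayed at 1.0-2.9% throughout. A pooled-variance version gave 3.0-4.9%.

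**6. Power at 6 vs 13 minutes, 136:68, equal log SDs.**

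| Log SD | Minutes, arm-specific variances | Site-level Wilcoxon | Subject-level Wilcoxon |
|---|---|---|---|
| 0.3 | 97% | 96% | 90% |
| 0.427 | about 72% | about 53% | 43% |
| 0.6 | 36% | 10% | 8% |

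**The case against.** **The plan intends logs, so the switch is not inevitable.** This has real support. SAP 8.5.2 repeats the rule for discharge eligibility but lists only normality. The added word in 8.5.1 therefore most naturally refers to TTH, since time to ambulation has a t-test. A reader might infer that Wilcoxon is bound to become the confirmatory test. That holds only on the minutes reading. On logs, the conflict with the minus-5 step remains.

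**The unit is stated.** Correct. Protocol 11.1.2 also specifies it: "first observed and confirmed venous hemostasis (per access site analysis"). SAP 8.8 averages sites for roll-ins ("Time to hemostasis will first be summarized across access sites within each subject"), but that is descriptive and covers non-randomised subjects, so it is weak evidence for a subject-level test. Applying the stated unit to an ordinary rank sum test is what creates the clustering problem.

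**The high error rates depend on chosen spreads.** Also correct. The SAP 5 model writes its variances without an arm index. Read on logs, this means equal log SDs, where the rank test is conservative and the sponsor loses power. The figure near 10% needs a pure shift, in which both arms cannot be lognormal. About 12% or more needs a larger log SD in the device arm, a ratio that no document gives.

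**Minutes are not the only valid choice.** Accepted. What is needed is one stated analysis that tests the stated hypothesis.

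**Conclusion.** The point stands as a defect of specification in a co-primary analysis. The response scale is not stated. The switch replaces a clustered model for a mean difference with a test that, at the stated access-site level, ignores clustering and in general answers a different question.

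On the assumptions listed, the site-level rank test's one-sided error at a true 5-minute difference is about 10% under a pure shift and about 0-2% with lognormal arms of equal log SD. In the lognormal cases run, it exceeded 2.5% only where the device log SD was the larger (about 12% at 0.5/0.3). At log SD 0.427, power at 6 vs 13 minutes is about 53% at site level or 43% at subject level, against about 72% for a test on minutes.

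A reader might infer two stronger conclusions that the documents do not support. One is that the plan favours the device: the direction depends on spreads that are not given. The other is that the stated 95% power is wrong: without an SD it cannot be checked.

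**What to change.** In SAP 8.5.1 and Protocol 16.9.1:

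- Remove the Shapiro-Wilk/Wilcoxon switch for TTH (it stands only in the SAP).
- State one primary analysis, with its scale, that tests the mean difference, keeps the 5-minute margin and accounts for sites within subject. One option is a linear mixed model in minutes with a random subject effect and subject-clustered (empirical) standard errors; another is a cluster-bootstrap interval. The pooled-variance result above is the reason for robust standard errors.
- Declare success if the lower one-sided 97.5% bound for control minus device exceeds 5 minutes.
- Keep a subject-level or clustered Wilcoxon test, on control times reduced by 5 minutes, as a sensitivity analysis only.
- State the SD behind the TTH sample size and restate power at 136:68 for the chosen test. The simulations with unequal site counts used a clustered mean difference, not the mixed model itself, so the re-run should use the exact model adopted.

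The cost is wording in two documents and a power re-run, with no new data and no change to conduct. The downside is that restated TTH power may fall below 95% if the spread is large.

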7 RANDOMIZATION

This is a randomized, controlled, open label study. Before the first subject is enrolled in the study, a randomization schedule will be generated by the study statistician and uploaded into an electronic database that can be accessed via computer. The schedule will be generated using a permuted block approach. Randomization will be performed at the conclusion of the index procedure, while the subject is on the table and the operator is able to visualize all access sites to verify eligibility. Since one of the primary endpoints of this study is time to ambulation, randomization will be done at the subject level to avoid the possibility of a subject receiving both MYNX CONTROL[™] Venous VCD and manual compression. Randomization will be stratified by study center with a 2:1 randomization ratio for MYNX CONTROL[™] Venous VCD vs. manual compression for access site closure.

Roll-in patients will not be randomized. All roll-in subjects will receive the MYNX CONTROL[™] Venous VCD.

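### The Shapiro-Wilk fallback for time to hemostasis (SAP 8.5.1) does not carry over the subject clustering; read per access site, its rank-sum test has about 10% one-sided error, not 2.5%, when the shifted arms are identical

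*SAP*

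**What the plan says.** SAP 8.5.1 covers both co-primary effectiveness endpoints. For time to ambulation (TTA), a t-test, it says "The test will be done on a per subject basis". For TTH it says "The average time to hemostasis will be analyzed on an access site level", using a mixed model with subject as a random effect. The TTH hypotheses concern a difference in means: the parameter "is the mean time to hemostasis for the indicated group and 5 minutes is superiority margin". To build in the margin, "The times to hemostasis in the manual compression group will be reduced by 5 minutes to account for the hypothesis".

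The section closes with one sentence for both endpoints: "If the distribution assumptions (normality, lognormality) for the primary effectiveness endpoints do not hold based on Shapiro-Wilk test at the 0.05 alpha level", then "a non-parametric Wilcoxon rank sum test will be used to compare the treatment groups". Nothing further is said about the fallback. Protocol 16.9.1 has no such fallback.

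Two other places bear on the unit. SAP 7 says "randomization will be done at the subject level to avoid the possibility of a subject receiving both" closure method. SAP 8.8, for roll-in subjects only, says "Time to hemostasis will first be summarized across access sites within each subject by calculating the mean time to hemostasis".

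**The concern.** The fallback can decide a co-primary endpoint. The planned mixed model allows for several access sites in one subject; an ordinary rank-sum test does not. The sentence that brings it in gives no handling of sites within subject. It also does not repeat the access-site unit or the 5-minute reduction, and it names normality and lognormality without assigning either to an endpoint or to raw, logged or shifted times.

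The natural reading, a rank-sum test on individual sites, treats correlated times as independent. The test could also be completed in different ways once the data are known, and those ways have different error rates. Separately, on either unit a rank-sum test does not address the stated hypothesis, a mean difference above 5 minutes.

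**Working it through.** **Inputs.** One-sided alpha 0.025 and 3 sites per subject (SAP 5); up to 4 sites (Protocol 16.8); compound symmetry, with within-subject variation about half of between-subject variation (SAP 5); allocation 136:68 (Protocol synopsis). If variation means variance, ICC = 1/(1+0.5) = 0.67; if it means SD, ICC = 1/(1+0.25) = 0.80. No SD for TTH is given, so a CV of 0.5, 0.75 or 1.0 in the device (VCD) arm is assumed, with lognormal times.

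The low end of that range is nearest the SAP's own power statement. With about 95% power at 100:50, shifted means of 6 v 8 and a common log SD s, the standard error is s × √[(0.667 + 0.333/3) × (1/100 + 1/50)] = 0.153s. Then s = ln(8/6)/(3.605 × 0.153) ≈ 0.52, a CV of about 0.56.

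**Step 1: the planned figure.** With 3 sites for everyone, the mixed model is equivalent to a t-test on subject means. In 20,000 simulated null trials it rejected in 2.56% (simulation SE 0.11), so the planned 2.5% is reproduced.

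**Step 2: site-level rank-sum test, identical shifted arms.** Ignoring clustering understates the variance by a factor of about 1 + (k−1) × ICC for k sites, so

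one-sided error ≈ 1 − Φ(1.96/√[1 + (k−1) × ICC]).

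For k = 3 and ICC = 0.667: 1 − Φ(1.96/1.528) = 1 − Φ(1.283) = 10.0%. Using the correlation of ranks, (6/π) × arcsin(0.667/2) = 0.649, gives 9.8%.

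| Sites | ICC 0.67 | ICC 0.80 |
|---|---|---|
| 2 | 6.5% | 7.2% |
| 3 | 10.0% | 11.2% |
| 4 | 12.9% | 14.4% |

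Simulation (4,000 trials per case, 3 sites, ICC 0.67) gives 9.3/10.5/10.4% for the three CVs. One mean per subject gives 2.2/2.2/2.5%.

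**Step 3: the whole two-stage rule, same setting.**

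| Shapiro-Wilk applied to | Fires in | Error, site-level fallback |
|---|---|---|
| Logged shifted times | 13.1/13.0/12.7% | 3.2/3.6/3.3% |
| Logged unshifted times | 79.5/90.9/96.5% | 7.5/9.7/10.1% |
| Raw minutes | 100% | 9.3/10.5/10.4% |

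A 30,000-trial run of the first row gives 3.5%. On the log scale, checking by arm or on conditional residuals instead moves it between 2.8% and 4.2%. With one mean per subject, the rule has 2.2-2.6% on all three scales.

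**Step 4: a true 5-minute difference (means 6 v 11), shifted, rank-sum test alone.**

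| | Equal SDs | Equal CVs |
|---|---|---|
| Per site | 15.0/12.2/8.7% | 0.7/0.1/0.1% |
| One mean per subject | 3.9/3.7/3.1% | 0.4/0.1/0.1% |
| Welch on subject means | 2.2/1.8/2.4% | 1.4/1.4/0.8% |

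Across runs the per-site, equal-SD figure lies at about 7-15%.

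Medians (mean/√(1+CV²)) show why the direction changes. At CV 0.5 the VCD median is 6/√1.25 = 5.37. With equal SDs (3 minutes), manual compression has CV 3/11 = 0.27 and a shifted median of 10.61 − 5 = 5.61, so the device looks better. With equal CVs, the shifted median is 9.84 − 5 = 4.84, so the device looks worse. The means differ by exactly 5 minutes in both cases.

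**Step 5: can shifted times be logged?** With equal CVs, P(manual-compression time ≤ 5) = Φ([ln 5 − ln 11 + s²/2]/s), where s² = ln(1+CV²). For CV 0.5/0.75/1.0, s = 0.472/0.668/0.833 and the share is about 8/20/30%. Those shifted times are zero or negative and have no logarithm.

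**The case against.** The strongest reply is that the section, read as a whole, settles most of this. The access-site unit is stated for TTH. The hypotheses carry the margin, so the reduction presumably still applies. Normality fits the TTA t-test, and lognormality fits the distribution assumed for TTH in SAP 5. On that reading the whole rule runs at about 3-4%, roughly a point over nominal.

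Much of this stands. A reader might infer that the unit is missing altogether; it is not, only not repeated in the fallback sentence. A reader might infer that the 5-minute reduction is dropped. In simulations with log SD 0.5 and 0.7, an unshifted test rejected in every trial at a true 5-minute difference, but the stated hypotheses do not support that reading. Nor does the SAP expressly order a site-level rank test. However, relying on the stated unit makes the clustering gap worse: the subject-level reading, at about 2.5%, rests only on the randomization unit and the roll-in summary and is the less supported one.

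The scale is also less settled than the reply suggests. SAP 8.5.1 does not say that TTH is logged for the model or the check, and logged shifted times may not exist for some sites.

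A second reply is that identical shifted arms is only one null. That is right. It makes observed manual-compression times a lognormal plus 5 minutes, which is not itself lognormal, and that is why the logged unshifted check fires so often. With equal CVs the rank test is very conservative, so a general claim of inflation would be wrong.

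**Conclusion.** Wrong as written, and it should be fixed. The fallback does not carry over the random subject effect. Read with the access-site unit, it replaces a clustered test of means with an unclustered test of ranks.

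Under the SAP's planning values (3 sites, ICC about 0.67 if variation means variance) and identical shifted arms, the site-level test has about 10% one-sided error against 2.5%. The whole rule has about 3-4% with logged shifted times checked and about 10% with raw minutes. At a true 5-minute difference, site-level error is about 7-15% with equal SDs and under 1% with equal CVs, so its direction depends on spreads the documents do not give.

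The CVs are assumed, and whole-rule error was worked out for identical shifted arms only. A reader might take 10% as the trial's false-positive rate. The documents do not support that: Protocol 16.9.1 makes success depend on TTA and safety as well, and all figures here are for TTH alone.

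**What to change.** Do not let an unclustered site-level rank-sum test decide TTH. State that any fallback respects clustering by subject and keeps the 5-minute reduction.

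Preferably test the mean difference against 5 minutes by a method that does not need normality: a Welch test on one mean per subject, or a cluster-robust confidence interval. Say which, and how subjects with different numbers of sites are weighted. Over 27 simulated null cases, including 1-4 sites per subject, both methods had 0.8-2.6% error. The Shapiro-Wilk switch is then unnecessary for TTH.

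Choosing a mean test is partly a preference. If a rank test is kept, use a clustered rank-sum test or one shifted mean per subject, and state the scale and data for the Shapiro-Wilk check. Treat it as supportive, because it does not test the stated mean hypothesis.

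The cost is SAP wording and programming, plus a power check with the sponsor's own SDs. At 6 v 13 (3 sites, ICC 0.67, CV 0.5/0.75/1.0), Welch has 100/93/74% power with equal SDs, against 100/99/92% for the subject-mean rank-sum test. With equal CVs it has 81/45/24%, against 57/14/3%. It can therefore lose or gain power against the rank test, and either can fall below the roughly 95% planned.
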